### 6.2.2 Secondary Safety Endpoints

- Occurrence of Early Onset (within 7 days of initial ablation) Serious Adverse Event
- Occurrence of Peri-Procedural (>7 to 30 days) Serious Adverse Event
- Occurrence of Late Onset (>30 days) Serious Adverse Event

## 6.3 Additional Endpoints

- 15-Month Effectiveness Success - Post Medication Adjustment Period (Day 91-450):
  - All AF Success: Clinical success is defined as freedom from documented all-cause (symptomatic and asymptomatic) AF/AFL/AT recurrence (episodes > 30 secs) between the end of the 3-Month Medication Adjustment Period and the 15-month follow-up visit (Day 91-450).

- Symptomatic AF Success: Clinical success is defined as freedom from documented symptomatic AF/AFL/AT recurrence (episodes  $\geq$  30 secs) between the end of the 3-Month Medication Adjustment Period and the 15-month follow-up visit (Day 91-450).
- 15-Month Effectiveness Success – Post Therapy Consolidation Period (Day 181-450):
  - All AF Success: Clinical success is defined as freedom from documented all-cause (symptomatic and asymptomatic) AF/AFL/AT recurrence (episodes > 30 secs) during the evaluation period (Day 181-450).
  - Symptomatic AF Success: Clinical success is defined as freedom from documented symptomatic AF/AFL/AT recurrence (episodes > 30 secs) during the evaluation period (Day 181-450).
- Procedural Data:
  - % PV isolation with the study device(s) by PV
  - Repeat Ablation Rate
  - Total Fluoroscopy Time
  - Overall Procedure Time
  - Duration of RF application time
  - RF Ablation parameters per application
  - Device(s) utilized (per ablation)
  - Duration of mapping time
  - VISITAG Settings
  - CF range
  - Power range
  - Ablation index Assessment per anatomical region
  - Ablation index data (Force, Power, and Time) will be collected in the CARTO® 3 system during the ablation procedures. The data will be processed to generate the ablation index.
- Quality of Life (QOL):
 

QOL status will be evaluated by assessing AFEQT and arrhythmia-specific Symptom Frequency and Severity Checklist outcomes

  - Quality of Life – AFEQT
  - AF Symptom Frequency and Severity Checklist
- Ablation Strategies Post-PVI:

Ablation strategies post PVI will be recorded during the AF ablation procedure. Safety and effectiveness of the ablation strategies employed post PVI will be characterized.

#### 6.4 Health Economic Data

Health economic data in this study includes:

- The cost and frequency of health care utilization during hospitalization for the study index ablation procedure, as well as any additional hospitalizations during the study period.
- The cost and frequencies of follow up care, including any repeat ablation procedure for treating arrhythmia, necessary procedures/surgeries resulting from procedure, ER visits, and outpatient visits to address issues related to arrhythmia or cardiovascular conditions.

### 7 Level of Significance

Only primary endpoints will be tested in this study. The hypothesis testing of this study will be performed at a significance level of two-sided 5%.

### 8 Analysis Sets

For the analysis of study endpoints, the analysis populations are defined as the following:

- **Modified Intent-To-Treat (mITT) Population:** the mITT population will consist of all enrolled subjects who meet all eligibility criteria AND in whom
  - (1) RF energy was delivered with study catheter OR
  - (2) Study catheter was inserted but no RF energy was delivered
- **Safety Population (SP):** The safety population will consist of all enrolled subjects who have undergone insertion of the study catheter. Safety endpoints will be analyzed based on the Safety Population.
- **Per Protocol (PP) Population:** The PP population will include subjects who satisfy the following criteria:
  - are enrolled and meet all eligibility criteria
  - have undergone RF ablation
  - are treated with the study catheters, and have been treated for the study-related arrhythmia

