3.1 Subject Selection

3.1.1 Inclusion Criteria

Candidates for this study must meet ALL of the following criteria:

1. Documented symptomatic persistent AF, which is defined as continuous AF sustains beyond 7 days and less than 1 year and is documented by the following:
 - a. Physician's note indicating continuous AF \geq 7 days but no more than 1 year;
AND
 - b. Two electrocardiograms (from any forms of rhythm monitoring) showing continuous AF, with electrocardiogram taken at least 7 days apart⁴ (electrograms cannot be >365 days prior to enrollment)
OR
 - c. 24-hour Holter within 90 days of the ablation procedure showing continuous AF
2. Failed at least one antiarrhythmic drug (AAD) (class I or III) as evidenced by recurrent symptomatic AF, or intolerable to the AAD.
3. Age 18 years or older.
4. Signed Patient Informed Consent Form (ICF).
5. Able and willing to comply with all pre-, post-, and follow-up testing and requirements.

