### **10.4 Primary Endpoints Analyses**

#### **10.4.1 Primary Effectiveness Endpoint**

The primary effectiveness endpoint is defined as achieving effectiveness success at 12 months after undergoing an RF ablation procedure using the THERMOCOOL® SMARTTOUCH™ SF catheter. The primary effectiveness rate will be compared to a pre-determined performance goal of 40%.

The primary effectiveness endpoint will be evaluated by constructing the two-sided 95% exact confidence interval for the effectiveness rate. If the lower bound of the exact confidence interval of the primary effectiveness endpoint rate is greater than the performance goal of 40%, the study will be considered to have demonstrated effectiveness of the device.

The per protocol population (PP) will be used as the primary analysis population for effectiveness. Subjects with missing effectiveness data during the 15-month follow-up period will be excluded from the primary analysis.

Analyses of the primary effectiveness endpoint will be repeated using the mITT population. Subjects with catheter inserted but no RF delivered due to investigational device deficiency in the mITT population will be categorized as effectiveness failures and included in the analysis. Subjects with no RF delivery due to other reasons (e.g. anatomical difficulty, complications) will be excluded from the mITT analysis and be included in the sensitivity analysis for missing data.

Sensitivity analyses for missing data will be performed using the PP and mITT populations to assess the impact of missingness on the primary effectiveness outcome and are outlined in section 10.4.3.

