### **10.4.3 Handling of Missing Data**

#### **10.4.3.1 Primary Effectiveness Endpoint**

Several sensitivity analyses will be performed to assess the robustness of results with regard to missing data for the primary effectiveness outcome. All analyses will be performed in the PP and mITT populations, which include but are not limited to the following:

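### PP and mITT share one eligibility filter, so no planned effectiveness estimate covers treated subjects found ineligible, and the mITT repeat cannot show whether leaving them out matters

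*SAP*

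**What the plan says.** SAP 8 and Protocol 7.1 define the three sets in the same way.

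- **mITT:** "the mITT population will consist of all enrolled subjects who meet all eligibility criteria AND in whom" RF was delivered with the study catheter, or the catheter was inserted and no RF was delivered.
- **PP:** subjects who "are enrolled and meet all eligibility criteria", underwent RF ablation, and were treated with the study catheter for the study arrhythmia.
- **Safety Population:** "The safety population will consist of all enrolled subjects who have undergone insertion of the study catheter". It has no eligibility condition, and SAP 8 assigns it to the safety endpoints.

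SAP 10.4.1 says "The per protocol population (PP) will be used as the primary analysis population for effectiveness", then "Analyses of the primary effectiveness endpoint will be repeated using the mITT population". It adds that "Subjects with no RF delivery due to other reasons (e.g. anatomical difficulty, complications) will be excluded from the mITT analysis"; those subjects come back only in the missing-data sensitivity analyses. For the latter, SAP 10.4.3.1 says "All analyses will be performed in the PP and mITT populations". The Kaplan-Meier analysis of recurrence (SAP 10.4.5.2) uses PP and mITT, and the secondary and additional effectiveness endpoints (SAP 10.5.1, 10.6.1, 10.6.2) use PP.

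SAP 4 states that there is no randomization or blinding. Neither document says who classifies eligibility for the analysis sets, from which data, or by when.

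**The concern.** A repeat in a second population is useful when it relaxes the exclusions of the first. Here it relaxes only the treatment conditions. Both sets drop anyone who fails an eligibility criterion, so agreement between PP and mITT says nothing about those subjects. The worst-case missing-data scenario does not bring them back either, because it runs inside the same two sets.

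The trial has one arm, no blinding and a fixed goal of 40%. A control group would be filtered by the same rule and would partly offset its effect; a performance goal is not. If the excluded subjects fail more often than the rest, the tested rate exceeds the rate among everyone treated, and no planned table would show the gap.

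**Working it through.** **Inputs from the documents.** Goal 40%, anticipated rate 50%, 330 subjects, at least 90% power, exact binomial (SAP 9.1). Two-sided 5% level (SAP 7). Success if the lower bound of the exact two-sided 95% interval exceeds 40% (SAP 10.4.1). Attrition 10%, enrolment 367 (SAP 9.3).

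**Input not in the documents.** The number k of treated subjects removed as ineligible. I take 1 to 17 of 330 (0.3% to 5%) as an assumption, and use 330 as the number treated for illustration.

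**1. The plan's own figures.** 330/0.90 = 366.7, rounded up to 367, as stated. At n = 330 the smallest passing count is 151 (45.8%), with exact lower bound 40.29%.
- P(X ≥ 151 | n = 330, p = 0.40) = 1.93%, the one-sided type I error.
- P(X ≥ 151 | n = 330, p = 0.50) = 94.5%, so the claim of at least 90% power is true.

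**2. Who is in which effectiveness estimate.**

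| Subject | PP | mITT | Safety Population |
|---|---|---|---|
| Eligible, RF with study catheter for the study arrhythmia | yes | yes | yes |
| Eligible, inserted, no RF | no | yes (scored as failure if device deficiency; otherwise only in missing-data analyses) | yes |
| Not eligible, RF with study catheter | no | no | yes |
| Not eligible, inserted, no RF | no | no | yes |

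The last two rows appear only in the set assigned to safety. The nearest exception is SAP 10.6.4, where the ablation index is characterized in PP and the Safety Population and may be correlated with effectiveness. That is optional and yields no success rate.

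**3. One subject at the boundary.**
- 150/330 = 45.45%, exact lower bound 39.99%: fails.
- 150/329 = 45.59%, exact lower bound 40.12%: passes.

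Classifying one treated failure as ineligible reverses the conclusion.

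**4. Worst case: only failures are removed.** Let c(m) be the smallest count that passes with m subjects. With 330 treated at a true 40% rate and k failures taken out, the trial passes if X ≥ c(330 − k), so type I error = P(X ≥ c(330 − k) | n = 330, p = 0.40).

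| k removed | Share of 330 | c(330 − k) | One-sided type I error |
|---|---|---|---|
| 0 | 0% | 151 | 1.9% |
| 1 | 0.3% | 150 | 2.5% (2.52%) |
| 3 | 0.9% | 149 | 3.2% |
| 5 | 1.5% | 148 | 4.1% |
| 10 | 3.0% | 146 | 6.5% |
| 17 | 5.2% | 143 | 11.9% |

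**5. Contrast: removal unrelated to outcome.** Taking out 3 to 33 subjects at random leaves type I error at 1.9% to 2.5% and power at 93% to 95%. The harm comes from a link between removal and outcome, not from the smaller sample.

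**6. How far an all-treated estimate could fall.** Suppose eligible subjects succeed at 50% and every ineligible subject fails.
- 1% ineligible: rate 0.50 × 0.99 = 49.5%, chance of passing at 330 is 92.2%.
- 2% ineligible: 0.50 × 0.98 = 49.0%, chance 89.1%.
- 5% ineligible: 0.50 × 0.95 = 47.5%, chance 75.4%.

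If ineligible subjects succeed at the same 50%, the chance stays at 94.5%.

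**The case against.** The strongest reply is that the trial studies the eligible population, and restricting the test to it is legitimate. If eligibility is settled on baseline facts, the PP test keeps its level for that population, and a lower rate among ineligible subjects is not bias. Protocol 3.0 has subjects satisfy all criteria before ablation, Protocol 1.3.2 has them screened before treatment, and Protocol 5.3 places the atrial-size measurement before the procedure. Treated but ineligible subjects are then screening deviations and probably few. This stands. It is why the PP test should remain primary and why the table in step 4 is a ceiling, not a forecast. It does not supply the missing estimate.

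A second reply is that the core laboratory protects the outcome. Protocol 5.19 has it read rhythm recordings; it is given no role in classifying eligibility.

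Three stronger readings are tempting, and the documents do not support them.
- *Subjects will be removed once their outcome is known.* The documents are silent on when the filter is closed. They neither plan nor describe such removal.
- *Poor follow-up could be recoded as ineligibility* through the criterion "Able and willing to comply with all pre-, post-, and follow-up testing and requirements". Protocol 3.1.1 applies it to candidates, as an entry judgement. Poor follow-up has its own categories (Protocol 3.2 to 3.4), and missing outcomes have their own analyses (SAP 10.4.3.1).
- *Ineligible subjects do worse, so the PP rate is biased upward.* SAP 10.4.5.1 lists atrial size and AF duration as covariates to explore and states no direction.

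**Conclusion.** The gap holds as a matter of definition: PP and mITT share the filter, every planned effectiveness rate uses one or both of them, and the mITT repeat cannot reveal the effect of the filter. Its size is unknown, because the documents give neither the number of treated but ineligible subjects nor their success rate.

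Two things bound it. At the boundary one reclassified failure is enough to change the conclusion. Under the stated worst case, type I error rises from 1.9% to between 2.5% and 11.9% for 1 to 17 removals. That range assumes 330 treated, a true rate of 40% and removal of failures only. If removal is unrelated to outcome, the effect is negligible. The safety analysis is not affected. This is a low-cost gap that should be closed, not a defect that invalidates the primary test.

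**What to change.** Keep the PP primary test unchanged.

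**SAP 10.4.1:** add a supportive repeat of the primary effectiveness analysis in all Safety Population subjects, regardless of eligibility. The set includes subjects with no RF delivered, who are followed for only 30 days (SAP 10.2), so a scoring rule is needed. Apply the rule already given for mITT: failure if the cause was an investigational device deficiency; for other reasons, excluded from this repeat and returned in the missing-data sensitivity analyses. SAP 10.4.3.1 must then name this set alongside PP and mITT.

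**SAP 8:** state that the PP and mITT eligibility filter uses only data recorded before catheter insertion, is decided by reviewers without access to any post-procedure effectiveness data, and is fixed before the effectiveness analysis. Withholding core-laboratory results alone would not be enough, because acute, repeat-ablation, AAD and surgical failures (Protocol 4.1.1) are known to the site without them.

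**Cost:** one extra table with its missing-data rows, and a few sentences in the SAP. The added estimate may be slightly less favourable than the PP result.

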4.0 STUDY ENDPOINTS

4.1 Primary Endpoints

4.1.1 Primary Effectiveness Endpoint

The primary effectiveness endpoint is defined as the freedom from documented atrial fibrillation, atrial flutter and atrial tachycardia (AF/AFL/AT) (hereinafter collectively referred to as "atrial tachyarrhythmias") recurrence (episodes ≥ 30 secs on Holter recordings/TTM or continuously recorded on the standard 12-leads ECG) during the evaluation period (Day 181-450) and freedom from the following failure modes:

- Acute procedural failure, including:
 - Failure to confirm entrance block in all pulmonary veins post-procedure,
 - Use of a non-study catheter to treat the study arrhythmia for the initial ablation procedure.

Device deficiency of a non-investigational device leading to the use of a non-study catheter (i.e., Stockert 70, SMARTABLATE™ RF Generator and COOLFLOW® Pump, SMARTABLATE™ Irrigation Pump), during the AF procedure will not be considered an acute failure.

- Non-study catheter failure:
 - Use of a non-study catheter to treat the study arrhythmia for repeat ablation procedure during the 3-Month Medication Adjustment or 3-Month Therapy Consolidation Periods.
- Repeat ablation failure, including:
 - > 2 repeat ablation procedures during the 3-Month Medication Adjustment Period / 3-Month Therapy Consolidation Period (Day 0-180) after the index procedure.
 - Any repeat ablation procedure during the Evaluation Period.

Refer to section 5.18 for details.

- AAD failure: Taking a new AAD or a previously failed AAD at a greater than the highest ineffective historical dose for AF during the evaluation period (refer to section 5.14 for details).
- Surgical failure: Undergoing surgical AF ablation or AF surgery any time after the index procedure.

In summary, effectiveness success is defined as freedom from atrial tachyarrhythmia during the Evaluation Period, off or on a previously failed AAD, and not exceeding 2 repeat ablation procedures for an atrial tachyarrhythmia during the 3-Month Medication Adjustment and 3-Month Therapy Consolidation Periods.

This study is designed to compare the primary effectiveness of the investigational device to a pre-determined performance goal of 40%, which is indicated as the minimum acceptable success rate at 12 months for a persistent AF population in the 2012 HRS

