### **6 Study Endpoints**

#### **6.1 Primary Endpoints and Associated Hypotheses**

##### **6.1.1 Primary Effectiveness Endpoint**

The primary effectiveness endpoint is defined as achieving effectiveness success after undergoing an RF ablation procedure using the THERMOCOOL® SMARTTOUCH™ SF catheter.

The null and alternative hypotheses are:

*Hypothesis:*  $H_0: P_E \leq 0.40$

$H_a: P_E > 0.40$

where  $P_E$  is the proportion of subjects who meet the effectiveness success criteria at 15 months follow-up

A subject has reached the effectiveness success if the subject is free from documented atrial tachyarrhythmia, including atrial fibrillation, atrial flutter and atrial tachycardia (AF/AFL/AT), recurrence (episodes  $\geq 30$  secs on Holter recordings/TTM or continuously recorded on the standard 12-leads ECG) during the evaluation period (Day 181-450) and free from the following failure modes:

- Acute procedural failure, including
  - Failure to confirm entrance block in all pulmonary veins post-procedure,
  - Use of a non-study catheter to treat the study arrhythmia for initial ablation,

- Non-study catheter failure while treating the study arrhythmia for repeat ablation procedure during the 3-Month Medication Adjustment or 3-Month Therapy Consolidation Period
- Repeat ablation failure, including
  - >2 repeat ablation procedures during the 3-Month Medication Adjustment Period / 3-Month Therapy Consolidation Period (Day 0-180) after the index procedure,
  - Any repeat ablation procedure during the evaluation period.
- AAD failure: Taking a new AAD or a previously failed AAD at a greater than the highest ineffective historical dose for AF during the evaluation period.
- Surgical failure: Undergoing surgical AF ablation or AF surgery any time after the index procedure.

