## 10.2 Subject Disposition

- **Enrolled Subjects:** subjects who sign the informed consent.
- **Excluded Subjects:** subjects who are enrolled but never undergo insertion of the study catheter.
- **Discontinued Subjects:** subjects have the investigational catheter inserted but do not undergo ablation (ie, no RF energy is delivered via the study device). These discontinued subjects will be followed up for 30 days.
- **Lost to Follow-up Subjects:** subjects who are enrolled and have study catheter inserted, but contact is lost after most recent follow-up visit (despite 3 documented attempts).
- **Withdrawn / Early Termination Subjects:** subjects who withdraw consent for study participation or are withdrawn by the investigator or are terminated from the study prior to completion of all follow-up visits.

- **Completed Subjects:** enrolled subjects who completed the 15-month follow-up visit.

Subject accountability and disposition will be summarized descriptively in all enrolled subjects.

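### A subject switched to a non-study catheter before any study-catheter RF is a listed failure, yet falls outside the primary per-protocol effectiveness analysis

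*SAP*

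**What the plan says.** **Endpoint.** Protocol 4.1.1 lists as an acute procedural failure "Use of a non-study catheter to treat the study arrhythmia for the initial ablation procedure"; SAP 6.1.1 has the same item ("Use of a non-study catheter to treat the study arrhythmia for initial ablation"). Protocol 4.1.1 makes one exemption. If a deficiency of a non-investigational device (generator or pump) led to the non-study catheter, its use "during the AF procedure will not be considered an acute failure". The SAP list does not repeat the exemption.

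**Primary population.** SAP 10.4.1: "The per protocol population (PP) will be used as the primary analysis population for effectiveness". Protocol 7.2.1 agrees. Under SAP 8 and Protocol 7.1, PP members are eligible, have undergone RF ablation, and "are treated with the study catheters, and have been treated for the study-related arrhythmia".

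**Study catheter inserted, no RF.** SAP 10.2 classes as discontinued, with 30 days of follow-up, those who have the catheter inserted but "do not undergo ablation (ie, no RF energy is delivered via the study device". SAP 10.4.1 deals with inserted/no-RF subjects only in the mITT repeat:
- "Subjects with catheter inserted but no RF delivered due to investigational device deficiency in the mITT population will be categorized as effectiveness failures".
- "Subjects with no RF delivery due to other reasons (e.g. anatomical difficulty, complications) will be excluded from the mITT analysis", after which the sentence sends them to the missing-data sensitivity analysis.

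**The concern.** The endpoint treats a catheter switch at the index procedure as the device failing to do its job. The primary population then requires that the study catheter did treat the subject. When the switch comes before any study-catheter RF, the event that makes the subject a failure also removes the subject from the analysis.

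The trial has one arm and a fixed 40% goal, so no control group would show a similar loss and offset it. For non-exempt switches, every subject removed is a failure, and the observed rate moves toward success. At stake is whether the primary success rate measures the endpoint as the sponsor defined it.

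**Working it through.** **1. Who is in and who is out.** All cases are eligible subjects with the study catheter inserted and a non-study catheter then used at the index ablation.

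| Case | Endpoint status | In PP? | mITT repeat |
|---|---|---|---|
| Some study-catheter RF, then switch | Failure | Yes, counted as failure | Failure |
| No study-catheter RF, investigational device deficiency | Failure | No | Failure, if the subject belongs to mITT |
| No study-catheter RF, other reason | Failure | No | Excluded, then handled as missing, if the subject belongs to mITT |
| No study-catheter RF, non-investigational device deficiency | Not a failure for the switch | No | Not clearly addressed |

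The proviso on mITT membership arises because limb (2) of the mITT definition speaks of no RF energy being delivered, without saying by which catheter; SAP 10.2 does specify the study device. A switched subject did receive RF, from another catheter, so may fit neither limb.

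Rows 2 and 3 are the problem: known failures that the primary analysis does not count.

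**2. The plan's own figures.** Inputs (SAP 9.1, 9.3, 10.4.1): goal 40%, anticipated rate 50%, n = 330, success if the exact two-sided 95% lower limit exceeds 40%. The critical count c(n) is the smallest c with P(X ≥ c | n, 0.40) ≤ 0.025.
- c(330) = 151 (45.8%, lower limit 40.29%), with tail probability 0.0193.
- Power = P(X ≥ 151 | 330, 0.50) = 94.5%. The stated power of at least 90% holds, although 330 exceeds the minimum: exact power first reaches 90% at n = 262 and stays there from n = 275.
- 330/0.90 = 366.7, rounded up to 367, as stated.

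The point does not depend on the sample size being larger than needed.

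**3. Chance of a false claim.** Assumptions: 330 subjects in all; k of them switched before study-catheter RF with no exemption, k being an assumed number; true success rate exactly 40% when those k count as failures. PP then has m = 330 − k subjects with success rate q = 0.40 × 330/m = 132/m. The false-success probability is P(X ≥ c(m) | m, q).

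| k | m | c(m) | q | False success |
|---|---|---|---|---|
| 0 | 330 | 151 | 40.00% | 1.9% |
| 3 | 327 | 149 | 40.37% | 3.2% |
| 7 | 323 | 148 | 40.87% | 4.0% |
| 10 | 320 | 146 | 41.25% | 6.3% |
| 16 | 314 | 144 | 42.04% | 9.5% |

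The limit in the deciding tail is 2.5%. Critical counts move in whole steps, so the rise is not smooth.

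**4. When the conclusion would change.** Exact lower limits:
- 148/330: 39.40%, fails. With five switched failures removed, 148/325: 40.03%, passes.
- From the boundary, adding excluded failures back: 151/332 gives 40.04%, passes; 151/333 gives 39.91%, fails. Three subjects (3/333 = 0.9%) are enough.
- From the expected result of 165/330 (44.48%): 165/335 gives 43.78% and 165/365 gives 40.02%, both passing; 165/366 gives 39.91%, failing. It takes 36.

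If the true rate is the planned 50%, the chance of 148 to 150 successes in 330, where removing five failures would turn a fail into a pass, is about 2.8%.

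**The case against.** The strongest reply is that the SAP already covers these subjects. Device-deficiency cases are failures in the mITT repeat. Those with other reasons go to the missing-data analyses of SAP 10.4.3.1, which include a worst case scoring every missing outcome as a failure and a tipping-point analysis replacing missing values with failures one at a time. A reader might infer that the plan never counts these subjects as failures; that would be wrong. What stands is narrower. These analyses are not primary. The PP versions cannot recover subjects who are not PP members. Handling the other-reason cases as missing sets aside an outcome that is known. And mITT membership is unclear for someone ablated with another catheter.

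Three further stronger readings are not supported:
- *The failure mode is emptied.* It is not. Nothing in the PP definition demands exclusive use of the study catheter, so a subject with some study-catheter RF before the switch stays in PP and fails.
- *The PP criterion can only raise the success rate.* It also removes exempt subjects with no study-catheter RF, some of whom might have been successes. The one-way direction holds for non-exempt switches only.
- *The trial's conclusion is in doubt.* No document gives a switch count. It may be very small, and a few subjects matter only near the boundary.

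Protocol 7.2.1 also says that subjects who failed before 15 months are included. That sentence stands in the paragraph naming PP as the population and follows the missing-data exclusion. It is best read as keeping early failures among PP members, not as changing membership. If more is intended, the two passages need reconciling.

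**Conclusion.** The point holds for the primary PP analysis and for one group: study catheter inserted, no study-catheter RF, non-study catheter used for the index ablation, exemption not applicable. The endpoint definition calls them failures and the population definition leaves them out, which favours success.

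The size depends on an unstated number. Over an assumed range of 0 to 16 in 330 (up to about 5%), with true success at the goal, the false-success probability runs from 1.9% to 9.5% and passes 2.5% by three subjects. A result near the expected 50% would be unaffected by a handful. The mITT repeat and its sensitivity analyses soften the problem without removing it. This should be corrected because the definitions conflict and the correction is easy; it does not show that the effectiveness claim would fail.

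**What to change.** **Primary analysis (SAP 8 and 10.4.1; Protocol 7.1 and 7.2.1).** State that eligible subjects with the study catheter inserted who are then ablated at the index procedure with a non-study catheter are included in the primary effectiveness analysis as acute procedural failures, whether or not study-catheter RF was delivered. Subjects under the non-investigational-device exemption are not scored as failures for the switch and keep the current PP rule. Repeat that exemption in SAP 6.1.1.

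**mITT.** Word limb (2) to say that no RF was delivered through the study catheter, and score the same non-exempt switched subjects as failures there, whatever the reason for the switch, instead of as missing.

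**Cost.** A few sentences in each document. The outcome is already fixed at the index procedure, so the 30-day follow-up of discontinued subjects is no obstacle. The success rate may be slightly lower, and a set called per protocol would contain some subjects the study catheter never treated, which the definition should say openly. If the anticipated 50% applies only to subjects treated with the study catheter, power at 330 falls from 94.5% to 92.5%, 89.0%, 85.6% or 76.8% with 3, 7, 10 or 16 switches counted as failures: P(X ≥ 151 | 330 − k, 0.50). If the 50% already allows for this failure mode, that loss does not arise.
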